7.0 Secondary Use or Sharing of Information or Contact Information

Storage for Future Use: All data collected will be stored for future use. This includes all assessment data. All assessment data will be stored separately from identifiable information. Assessment data are coded with a unique study ID number, which cannot be used to identify the participant; the ID number will be stored along with the assessment data for future use. De-identified Talkspace treatment data that has been merged with assessment data will be stored for future use, and this merged data set will be coded with unique IDs that are distinct from, stored separately from, and not linked to the original separate data sets.

Data Sharing: All assessment data may be shared with other researchers. No direct identifiers will be shared. Participants consent to this sharing during the provision of informed consent. De-identified content and meta-data may also be shared with other researchers. Patients agree to this as part of Talkspace's Privacy Policy before they enter the platform and the study.

Oversight/management of Sharing: The oversight and management of this sharing will be the responsibility of project Pls.

Possible Future Uses: Possible future uses include ongoing data analysis for publication and informing future grant proposals for clinical trials.

8.0 Statistical Analysis Plan

Phase 1: We will compute descriptive statistics associated with confidence intervals that summarize recruitment rates, proportions completing instruments, attrition rates and time to drop out, missing data, and mean scale scores over time. Estimates of longitudinal change and condition-difference effect sizes will be computed. Comparisons will be conducted using pairwise methods, instead of omnibus ones, in order to highlight those groups that appear different. To determine the best incentive model for this study, we will calculate the proportion of the sample that completes daily, weekly and follow-up assessments. This will be benchmarked against what is considered acceptable retention in clinical trials, which is typically greater than 75% retention rates from baseline to final endpoint analysis, with an ideal of 80% retention. In preliminary study A3B (Baseline Mood Study), we were able to retain 80% of the sample providing 98% of all assessments with an incentive value of \$125 for a 12-week engagement. Should the low-incentive+feedback arm fall below this benchmark, we will use the incentive value of \$125 per participant in Phase 2. If we meet this target, we will use the incentive value of \$75 plus feedback per person in Phase 2. To determine overall drop-out rate, we will calculate the proportion who stop treatment but complete all assessments, and the proportion who drop from the study overall. Additionally, we will calculate whether there is a significant difference in drop-out rates among the two incentive arms and four treatment arms using Pearson's chi-square test. To calculate time to drop out, we will estimate and test a survival analysis model. The distribution of the 'survival' times for those assigned each incentive and treatment arm will be estimated, and nonparametric estimates of the survivor function will be computed by the Kaplan-Meier method. Curves will be tested using the log-rank and Tarone-Ware tests. Covariates, including baseline measures, will be included as covariates to test for their relationship to the survival function.

Phase 2: Phase 2 is a 12-week, randomized clinical trial using a sequential multiple assignment randomized trial (SMART) design (see protocol paper¹¹ and incentive paper¹²). Its goals are to:

1. Test effectiveness of unlimited daily, message-based psychotherapy (MBP) for depression, compared to weekly traditionally delivered, videoconferencing-based psychotherapy (VBP). Level 1 conditions: unlimited MBP and weekly VBP.
2. Develop an evidence-based treatment sequence for those who do not respond to either MBP or VBP. Level 2 conditions for participants who do not respond to treatment: MBP+VBP_{weekly} (switch from MBP to weekly VBP with MBP), MBP+VBP_{monthly} (switch from MBP to monthly VBP with MBP), VBP_{weekly}+MBP (switch from VBP to weekly VBP with MBP), and VBP_{monthly}+MBP (switch from VBP to monthly VBP with MBP).

Hypothesis 1: Compared to those randomized to weekly video care at baseline, patients randomized to message-based care will have greater improvements in depression (1a) and social functioning (1b), be more likely to show a treatment response (1c), and be more likely to experience remission (1d) at 5 and 12 weeks of care. Hypothesis 2: For those who fail to respond to treatment from baseline to 5 weeks, those re-randomized to receive (or retain) weekly video care will have greater improvements in depression and be more likely to show a response to treatment than those randomized to monthly video care. Hypothesis 3 (moderator): Baseline anxiety will moderate improvement in depression such that those with greater anxiety will have better response to message-based care at 5 and 12 weeks than to video-based care. Exploratory Aims: Exploratory evaluation of differences among groups in treatment engagement by week 5, ratings of therapeutic alliance at weeks 4 and 10, ratings of

quality of care and amount helped by treatment at week 10, and ratings of goal satisfaction, plans to continue using treatment, and likelihood to recommend treatment to others at week 12.

Sample Size and Power: We propose to screen 4,789 potential participants, anticipating we will enroll 1,250 participants to arrive at a final sample of 1,000 evaluated participants, assuming a 20% dropout rate by the last assessment. In our previous psychotherapy studies, dropout rates have been on the order of 10% by final assessment. In our recent on-line studies with Google Verily, drop out has been on the order of 20%. Our large incentive arm, tested in Phase 1, is based on the incentive analyses done on the Baseline Mood Study at Verily.

Level 1 Power: For the quantitative primary outcome (PHQ-9) we have greater than 80% power to detect a 0.20 standard deviation across groups which corresponds to a clinically meaningful small difference. For a binary success indicator, we will consider a 50% reduction in PHQ-9 from baseline to week 5, and we have greater than 80% power to detect an absolute difference of 10% (e.g., 60% of subjects with >50% improvement versus 70% of subjects with >50% improvement).

Level 2 Power: The primary comparison in the second stage is the comparison of the Ultimate Plan (UP; MBP with weekly VBP) versus the Premium Plan (PP; MBP with monthly VBP) for each of the first stage randomization groups (MBP and VBP). We expect a second stage analysis sample of 324 subjects, and this corresponds to 80% power to detect a 0.32 standard deviation difference across the UP and PP groups when pooling across the primary MBP and VBP strata. Our primary second stage analysis will construct an overall UP versus PP difference stratifying on first stage randomization, and secondary analysis will consider the UP versus PP difference within the MBP and VBP groups separately.

Accounting for Provider Effects: Each provider will treat both MBP and VBP patients. Therefore, our primary analyses will all cluster on provider either using linear mixed models or generalized estimating equations to yield valid statistical inference. However, since treatment condition will vary within provider, the impact of provider clustering is to effectively balance or control for provider effects. Therefore, our power calculations are conservative since they do not account for the potential increase in precision associated with control for provider effects. Such within-provider randomization is in contrast to traditional cluster randomized trials where providers treat all patients in one study condition and thus increase variability associated with treatment comparisons through the well-known intra-cluster correlation coefficient.

Statistical Analyses: See Table 2 for analyses by hypothesis. Treatment disengagement, treatment response, and remission will be analyzed using chi-square tests and Cramér V effect sizes. 2-level linear mixed effects models using full information maximum likelihood (FIML) and an unstructured covariance matrix with client nested within clinician will be used for analyses at a single timepoint. Models predicting binary outcomes at a single timepoint will be evaluated using 2-level logistic regression models with Cholesky factorization with client nested within clinician, with Level 2 condition as the independent variable. Effect sizes for these models will be computed via pooled standard deviations of conditions at that timepoint.

Models assessing changes across time will be evaluated using 3-level mixed effects regression models with timepoint nested within client nested within clinician using FIML and an unstructured covariance matrix. Client-level effects will be allowed to randomly vary, and clinician will be a clustering variable with condition approximately balanced within clinicians. Analyses with time from baseline to week 12 will include a spline variable to account for differences in outcome trajectories from baseline to week 5 and from week 6 to week 12.

The mixed-effects models will utilize all available data. Prior research has demonstrated equivalence of longitudinal mixed model analyses using imputed versus non-imputed data (e.g., between multiple imputation and FIML).¹³ Theoretically, there is no reason to expect substantial differences between FIML and MI with a reasonable sample size and complete predictors.¹⁴ Thus, missing data will not be imputed. Cohen's *d* clinical outcome effect sizes for the model predicting PHQ-9 scores by Level 2 condition from weeks 6 to 12 will be computed as the difference between model-estimated means divided by the pooled standard deviations when the second condition

was assigned at week 6. All remaining clinical outcome effect sizes will be computed as the difference between model-estimated means divided by the pooled baseline standard deviations.

We will use the Benjamini-Hochberg procedure to account for Type 1 error by adjusting for familywise error within hypothesis families (e.g., within Hypotheses 1a to 1d; within Hypothesis 2). *P* values and effect sizes with 95% confidence intervals will be reported, as appropriate.¹⁵

Table 2. Analyses by Hypothesis

Hypothesis	Timepoint(s)	Statistical Test	Contrast/analysis of interest
1a: Compared to those randomized to weekly video care at baseline, patients randomized to message-based care will have greater improvements in depression	Baseline to W5	3-level mixed effects model	MBP vs VBP
1b: Compared to those randomized to weekly video care at baseline, patients randomized to message-based care will have greater improvements in social functioning	Baseline to W12	3-level mixed effects model	MBP vs VBP
1c: Compared to those randomized to weekly video care at baseline, patients randomized to message-based care will be more likely to show a treatment response at 5 and 12 weeks of care.	Between W3 to W5 / W12	Chi-square tests	MBP vs VBP
1d: Compared to those randomized to weekly video care at baseline, patients randomized to message-based care will be more likely to experience remission at 5 and 12 weeks of care.	Between W3 to W5 / W12	Chi-square tests	MBP vs VBP
2: For those who fail to respond to treatment from baseline to 5 weeks, those re-randomized to receive (or retain) weekly video care will have greater improvements in depression than those randomized to monthly video care	W6 to W12	3-level mixed effects model with time centered at week 6	MBP+VBP _{weekly} vs MBP+VBP _{monthly} ; VBP _{weekly} +MBP vs VBP _{monthly} +MBP
2: For those who fail to respond to treatment from baseline to 5 weeks, those re-randomized to receive (or retain) weekly video care will be more likely to show a response to treatment than those randomized to monthly video care	W12	Chi-square test	MBP+VBP _{weekly} vs MBP+VBP _{monthly} ; VBP _{weekly} +MBP vs VBP _{monthly} +MBP
3 (moderator): Baseline anxiety will moderate improvement in depression such that those with greater anxiety will have better response to message-based care at 5 and 12 weeks than to video-based care.	Baseline to W12	3-level mixed effects model, with mean-centered baseline GAD-7	MBP vs VBP

Exploratory: We will explore whether there will be differences among groups in treatment engagement by week 5	Between W3 to W5	Chi-square test	MBP vs VBP
Exploratory: We will explore whether there will be differences among groups in ratings of therapeutic alliance	W4 / W10	2-level mixed effects models	W4: Level 1 conditions (MBP vs VBP); W10: Level 2 conditions (MBP vs VBP; MBP+VBP _{monthly} vs MBP+VBP _{weekly} ; VBP _{monthly} +MBP vs VBP _{monthly} +MBP)

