3.0 Study Design

Phase 1 and Phase 2: Remote, randomized clinical trial using a 12-week, longitudinal SMART (Sequential Multiple Assignment Randomized Trial) design.

Phase 1, LEVEL 1 Randomization: Participants will be randomized to one of two conditions after completing baseline assessments: high monetary incentive and low monetary and feedback. After they are randomized to an incentive arm, they will then be randomized to either MBP or VBP. After six weeks of treatment, participants will move to level 2.

[figure not shown]
Phase 1, LEVEL 2 Randomization: Those who have made a 50% reduction to Patient Health Questionnaire-9 (PHQ-9)² scores to their assigned treatment will continue in that same treatment for 6 more weeks. Participants randomized to VBP who do not show 50% reduction in PHQ-9 scores will be randomized to either weekly VBP augmented with unlimited MBP (augmentation arm) or monthly VBP with unlimited MBP (switch arm).

Participants randomized to MBP who do not show a 50% reduction in PHQ-9 scores will be randomized to either unlimited MBP with weekly VBP (augmentation arm) or unlimited MBP and monthly VBP (minimal augmentation). The decision to switch or augment treatment after there is no response to treatment (described as a <50% change in PHQ-9 score) is based on treatment recommendations from the American Psychological Association, The

National Health Service in the UK, and the AHRQ depression guidelines. The Talkspace therapists, operating as consulting members of the study team, will complete the Clinical Global Impression – Improvement Scale after 5 weeks of treatment; if the participant does not complete a PHQ-9 in a timely manner for Level 2 randomization, this scale will be referenced for determining appropriateness for Level 2 randomization.

Phase 2, LEVEL 1 Randomization: Participants will be randomized to either MBP or weekly VBP. After six weeks of treatment, participants will move to Level 2.

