Phase 1: See Section 3.0. Randomization will be determined using www.randi2.org, an open-source web-based RCT randomizer that supports many types of algorithms (complete, biased coin, truncated randomization, block randomization, and the Wei's urn model randomization). Participants will be randomized to the first level of care using Wei's urn randomization blocking by recruitment, which adapts the probability of randomization to condition by the balance in the group assignments. This tightly controls balance while permitting randomization. Level 1 participants who respond to treatment will continue in their baseline condition. Level 1 participants who do not respond to treatment by week 5 (PHQ-9 score > 50% of baseline PHQ-9 score, or CGI-I score >2) will be re-randomized to receive MBP and supplemental weekly or monthly VBP.

Phase 2: See Section 3.0. Baseline Level 1 randomization to MBP or VBP occurred on REDCap and will be triggered by a research coordinator upon enrollment. We will use simple randomization with pre-specified and concealed blocks by therapist. Level 2 randomization will occur on REDCap. Level 1 participants who respond to treatment will continue in their baseline condition. Level 1 participants who do not respond to treatment by week 5 (PHQ-9 score > 50% of baseline PHQ-9 score, or CGI-I score >2) will be re-randomized to receive MBP and supplemental weekly or monthly VBP.

Treatment Procedures: All procedures described here are methods developed and used by Talkspace, unless otherwise specified. There are four interventions in this study: Level 1 interventions are unlimited MBP and weekly VBP. Level 2 interventions are MBP with monthly VBP, and MBP with weekly VBP. After participants give consent to participate, they will be randomized to one of the two Level 1 conditions. As per Talkspace's model, participants are offered a choice of three therapists, based on the state the therapist is licensed in. Procedures for consumer/clinician initiation are the same for each treatment option. Participants can contact their therapists any time after they are provided with choices. Once participants reach out to a therapist, therapists connect within 15 minutes to 24 hours, depending on the time of day the participants made their choice and the therapists' office

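### Phase 1 drop-out is to be compared across four undefined treatment arms; if these mix Level 1 and Level 2, the comparison is biased towards lower drop-out in Level 2

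*Combined protocol and SAP*

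**What the plan says.** The Phase 1 part of section 8.0 (Statistical Analysis Plan) tests for a "significant difference in drop-out rates among the two incentive arms and four treatment arms", by Pearson's chi-square. For time to drop-out it adds: "The distribution of the 'survival' times for those assigned each incentive and treatment arm will be estimated". Those curves are Kaplan-Meier estimates, tested by log-rank and Tarone-Ware. The same paragraph prefers pairwise to omnibus comparisons. It names two kinds of drop-out: stopping treatment while still completing assessments, and leaving the study altogether.

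Section 8.0 does not list the four arms. Section 5.1 (Treatment Procedures) gives the document's only explicit count of four treatments: "There are four interventions in this study: Level 1 interventions are unlimited MBP and weekly VBP", and "Level 2 interventions are MBP with monthly VBP, and MBP with weekly VBP".

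The Level 2 treatments come later and go to a selected group. Section 3.0 says for Phase 1: "After six weeks of treatment, participants will move to level 2". Section 5.1 (Randomization) says: "Level 1 participants who respond to treatment will continue in their baseline condition". Only those classed as non-responders by week 5 are re-randomised.

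The Phase 1 plan states no time origin, landmark, delayed entry or time-dependent treatment.

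**The concern.** If the four arms are the four interventions of section 5.1, they are not four groups formed by one randomisation. A participant who leaves the study in week 3 can be counted only under MBP or weekly VBP. A participant counted under a Level 2 treatment has, in most cases, already stayed about six weeks. Early losses therefore accumulate in Level 1, and Level 2 begins with people who stayed. This is immortal-time bias. The groups also differ by response status, which is itself a result of the first six weeks.

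What is at stake is the reading of Phase 1 retention by treatment. A lower drop-out rate in the two combined treatments could be taken as an effect of treatment when it comes from the way people were assigned to groups.

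**Working it through.** **Inputs from the document**
- Phase 1 size: 200 (section 4.2).
- Drop-out by the last assessment: 20% (section 8.0, Phase 2 sample size). It agrees with the 80% retention ideal in the Phase 1 text. As a check, 1,000 / (1 − 0.20) = 1,250, which is the plan's Phase 2 enrolment figure.
- Non-response: 30% to 40%, from the Level 1 power example of 60% versus 70% responding. The expected second-stage sample agrees: 324 / 1,000 = 32.4%.
- Phase 1 states no power or error rate, so there is no plan figure for this test to reproduce.

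**Assumptions not in the document**
- The drop-out hazard is constant and the same for everyone, and drop-out is independent of response. Treatment therefore has no effect.
- Non-responders still in the study at week 6 are re-randomised 1:1.
- Each person is counted in the last arm assigned.
- Alpha is 0.05.

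**Expected drop-out by level**

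Retention to week 6 is √0.80 = 0.8944, so drop-out in each six-week half is p = 1 − 0.8944 = 0.1056. With non-response r, the share reaching Level 2 is s = 0.8944 × r. Level 2 drop-out is p = 10.6%. Level 1 drop-out is (0.20 − s × p) / (1 − s).

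| r | s | People in Level 2 (of 200) | Level 1 drop-out | Level 2 drop-out |
|---|---|---|---|---|
| 0.30 | 0.2683 | 53.7 | (0.20 − 0.0283) / 0.7317 = 23.5% | 10.6% |
| 0.35 | 0.3130 | 62.6 | (0.20 − 0.0330) / 0.6870 = 24.3% | 10.6% |
| 0.40 | 0.3578 | 71.6 | (0.20 − 0.0378) / 0.6422 = 25.3% | 10.6% |

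**False rejection at nominal 5%** (simulated trials of 200 people under this null)
- Four-group chi-square: about 32% to 53% for r from 0.30 to 0.40, and 41.5% at r = 0.35.
- Four-group log-rank with the clock starting at baseline: about 34% to 56%, and 44.7% at r = 0.35.
- Pairwise chi-square: four of the six pairs cross levels, and each of these rejects about 28% to 43% of the time. The two within-level pairs hold about 5%.

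**Sensitivity** (20% drop-out and r = 0.35 unless stated)

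| Change | False rejection |
|---|---|
| Drop-out 10% to 40%, r 0.35 to 0.50 | chi-square 18.7% to 95.0% |
| Three quarters of drop-out before week 6 | chi-square 83.1% |
| Half of early drop-outs still re-randomised | chi-square 10.1% |
| All early drop-outs still re-randomised | chi-square 5.0% |
| Level 2 clock starts at week 6 | log-rank 6.3% (23.2% at r = 0.50) |
| Level 2 clock starts at week 6, three quarters of drop-out early | log-rank 56.0% |
| Four arms are the four re-randomised cells | chi-square 3.9% |

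**Alternatives under the same null** (20% drop-out, r = 0.35)
- Level 1 as randomised: 4.7%.
- Weekly versus monthly among the re-randomised, pooled over Level 1 arm: 5.3%.
- Four-arm chi-square among those still in the study at week 6: 4.3%.
- Log-rank with time-dependent treatment: 4.7%.

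**The case against.** The strongest reply is that the arms are undefined. Section 5.1 counts interventions, not arms. The Phase 1 text of section 3.0 describes four re-randomised cells: two following VBP and two following MBP. If those are meant, this bias does not arise. That stands as a possible reading. It would, however, leave out every responder and everyone lost before week 6, which fits poorly with a paragraph on overall drop-out. Crossing the two incentives with the two Level 1 treatments also gives four groups, all formed at baseline, but section 8.0 names the incentive arms separately.

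Entry to Level 2 is also not strictly confined to people who have not dropped out. Section 3.0 lets the therapist's CGI-I rating replace a PHQ-9 that is not completed in time. Someone who stops treatment but keeps completing assessments can also still be classed as a non-responder and re-randomised. The bias therefore applies chiefly to leaving the study altogether. The plan does not say how often the CGI-I route would be used.

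The clock start is likewise unstated. Timing Level 2 from re-randomisation removes most of the log-rank inflation in the base case, though not if drop-out is mostly early. The stated preference for pairwise methods protects only the two within-level pairs.

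A reader might infer that these tests are bound to show false differences. The figures do not support that: at 20% drop-out and 30% to 40% non-response the four-group chi-square still fails to reject about 47% to 68% of the time. A reader might also infer that Phase 1 will conclude that adding video to messaging improves retention. Nothing in the document says so. The treatment-arm comparison has no decision attached, and the stated Phase 1 purpose is the choice of incentive.

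**Conclusion.** The concern holds in a conditional form. Section 8.0 leaves the four arms and the time origin undefined. On the most natural reading, the two Level 1 and two Level 2 interventions, comparisons across levels are biased towards lower drop-out in Level 2. Under the stated assumptions the artificial gap is about 13 to 15 percentage points (23.5% − 10.6% = 12.9; 25.3% − 10.6% = 14.7), and the four-group chi-square rejects falsely about 32% to 53% of the time.

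The size rests on constant hazard, drop-out independent of response, and last-assigned-arm counting. A different drop-out risk among non-responders could narrow or widen the gap. The bias shrinks with use of the CGI-I fallback or a Level 2 clock that starts at re-randomisation, and it is absent if the four re-randomised cells are meant.

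The incentive-arm comparison is randomised at baseline and is not touched, so the choice of Phase 2 payment is not in question. The change should be made, but it does not threaten the main purpose of Phase 1.

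**What to change.** In the Phase 1 part of section 8.0, replace the four-arm comparison with two, and state which kind of drop-out each uses:

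1. Drop-out and time to drop-out from baseline to week 12 by Level 1 arm as randomised, keeping re-randomised participants in their original arm.
2. Among re-randomised participants, drop-out and time to drop-out from the re-randomisation date, weekly versus monthly video, stratified by Level 1 arm.

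Make no test across levels unless it uses a week-6 landmark or time-dependent treatment. Label any such test as non-randomised: these methods deal with the early losses, but the groups still differ by response status.

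The cost is a change of SAP wording and, if needed, a re-run on existing data. The drawback is that the second comparison is smaller (about 54 to 72 people under the assumptions above) and covers follow-up only from re-randomisation. Section 4.5 indicates that Phase 1 has already informed Phase 2, but the document does not show how drop-out by treatment arm was analysed. Any such result should be checked before it is cited.

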This study will have commercial impact in that it will be the first to determine the relative effectiveness of unlimited, asynchronous MBP compared to more traditional VBP. Thus, this study will make a significant public health impact by being the first to evaluate a commercial product delivering MBP compared to VBP and addresses NIMH strategic priority area 4.1 (improve the efficiency and effectiveness of mental health services through research). Second, this study will have an impact on clinical care in that it will be able to determine the best digital treatment algorithm for people who do not respond to either MBP or VBP only and who respond to VBP, MBP, or the combination. There has been considerable interest in the clinical and policy realm in understanding who responds to different levels of care, and when patients should be "stepped up" in intervention intensity. Thus, this study will make a significant clinical impact by identifying a treatment sequence for systems that provide teletherapy and is responsive to NIMH priority area 3.2 (develop ways to tailor existing and new interventions to optimize outcomes).

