1.2 Study Aims

This fast-track Small Business Innovations Research (SIBR) aims to (1) determine the relative effectiveness of unlimited MBP, compared to weekly VBP, (2) determine whether a switch to monthly VBP+MBP or weekly VBP+MBP is better for people who do not respond to VBP or MBP alone; (3) determine who responds to best to VBP, MBP, or the combined conditions, and (4) test the assumptions about the frequency and timeliness of treatment on working alliance and hence treatment outcomes.

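### The trial claims it will identify a treatment sequence, but no planned Phase 2 analysis estimates or compares the four whole start-plus-step-up sequences

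*Combined protocol and SAP*

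**What the plan says.** **What is promised.** Section 1.1 states that "this study will make a significant clinical impact by identifying a treatment sequence for systems that provide teletherapy". It also says that "it will be able to determine the best digital treatment algorithm for people who do not respond to either MBP or VBP only", and the same sentence goes on to cover people who do respond to video, messaging or both. The formal aims are narrower. Aim 2 in Section 1.2 is to "determine whether a switch to monthly VBP+MBP or weekly VBP+MBP is better for people who do not respond to VBP or MBP alone", and goal 2 of the Phase 2 SAP (Section 8.0) is to "Develop an evidence-based treatment sequence for those who do not respond to either MBP or VBP".

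**What the design contains.** Participants start on MBP or weekly VBP. Under Section 5.1, "Level 1 participants who respond to treatment will continue in their baseline condition"; non-responders are re-randomised to MBP with weekly or with monthly VBP. Two starts and two step-ups give four embedded sequences.

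**What is analysed.** Hypothesis 1 compares MBP with VBP by initial assignment. Hypothesis 2 compares weekly with monthly step-up among non-responders. Under Level 2 Power, "Our primary second stage analysis will construct an overall UP versus PP difference stratifying on first stage randomization", with the comparison inside each start as secondary; Table 2 lists the within-start pairs. Hypothesis 3 tests whether baseline GAD-7 moderates the MBP versus VBP effect. The exploratory rows reuse these contrasts for other outcomes.

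**The concern.** A teletherapy service that adopts a treatment policy chooses a start and a step-up rule together. The outcome of that policy combines the people who respond and stay with the people who do not respond and step up, in the proportions that the start produces. Neither stage's comparison gives this quantity. The week-12 start comparison mixes the two step-ups, and the step-up comparison leaves out responders and never crosses starts. The winner of each stage, taken separately, need not form the best whole sequence.

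At stake is one of the stated deliverables. As planned, the final report could not give the expected week-12 PHQ-9 for any of the four policies, or the difference between two of them. An analysis added after the results are known would be open to selection.

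**Working it through.** **1. Planned contrasts set against the four sequences (SAP Section 8.0 and Table 2)**

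| Planned analysis | Population | Contrast | Gives a whole-sequence result? |
|---|---|---|---|
| 1a (Table 2: to week 5); week 3–5 parts of 1c and 1d | All randomised | MBP vs VBP | No: precedes any step-up |
| 1b to week 12; week-12 parts of 1c and 1d | All randomised | MBP vs VBP | No: averages over step-ups |
| Hypothesis 2 | Non-responders | Weekly vs monthly, pooled with stratification on start, and within start | No: responders left out, starts not crossed |
| Hypothesis 3 | All randomised | GAD-7 moderation of MBP vs VBP | No |
| Exploratory, weeks 10 and 12 | By Level 2 condition | Within-start pairs; MBP vs VBP | No. If MBP vs VBP means those who stayed on their start, it compares responders only |

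No row combines responders and non-responders by sequence, gives weights, contrasts sequences with different starts, or has a power statement for such a contrast.

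**2. The plan's own power figures**

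Two-sided alpha of 0.05 and 1:1 allocation are assumed, because the power text states neither.

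- Level 2: 324 subjects, 162 per arm. Detectable difference at 80% power = 2.802 × √(2/162) = 0.311 SD. Power for the stated 0.32 SD is 82%, so the stated 80% is reproduced.
- Level 1: 500 per arm. Power is 88.5% for 0.20 SD and 91.3% for 60% versus 70%, in line with the stated figure of more than 80%.
- Within one start, with an even split assumed, there are 81 per arm. Detectable difference = 2.802 × √(2/81) = 0.440 SD; power for 0.32 SD is 53%.

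**3. Precision of a sequence comparison**

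The plan gives no figure, so this one is illustrative. Inputs: N = 1,000 evaluated (Sample Size and Power) and q = 324/1,000 = 0.324 non-response. Setting the 324 against the 1,000 is an assumption. Also assumed: 1:1 at both levels, and the same outcome SD in every group.

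- Contributors to one sequence: N(1−q)/2 responders and Nq/4 non-responders.
- Variance of a sequence mean, in SD² = [2(1−q) + 4q]/N = (1.352 + 1.296)/1,000 = 0.002648. The effective sample size is 1/0.002648 ≈ 378.
- Two sequences with different starts: SE = √(2 × 0.002648) = 0.0728 SD.
- Detectable at 80% power, unadjusted: 2.802 × 0.0728 = 0.204 SD.
- Detectable with Bonferroni over six pairs (z = 2.638 + 0.842 = 3.480): 3.480 × 0.0728 = 0.253 SD.
- Power for 0.20 SD: 78.5% unadjusted, 54.4% with Bonferroni.
- Two sequences with the same start share their responders, so they differ only through non-responders: 0.440 × 0.324 = 0.143 SD on the whole-sequence scale, unadjusted.

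| Non-response q | Detectable, unadjusted | Detectable, Bonferroni over 6 |
|---|---|---|
| 30% | 0.202 SD | 0.251 SD |
| 32.4% | 0.204 SD | 0.253 SD |
| 40% | 0.210 SD | 0.260 SD |
| 60% | 0.224 SD | 0.278 SD |

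**The case against.** The strongest reply is that the formal goals do have a matching analysis. Goal 2 and Aim 2 concern non-responders. Once a patient has not responded, the start is fixed and only the step-up remains to be chosen, which is what Hypothesis 2 tests. The second stage is sized for that question, and stage-by-stage questions are a coherent use of a SMART. This stands. What remains is the wider claim in Section 1.1 and the fact that no planned estimate serves it.

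Several stronger readings are tempting, and the documents do not support them:

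- *That the trial cannot compare sequences.* This is true of the listed analyses, not of the design, whose two randomisations would support the comparison.
- *That all of Hypothesis 1 is blurred by the step-ups.* Only its week-12 parts are; the week-5 parts come before re-randomisation. An even mix of step-ups is also an assumption, since no Level 2 ratio is stated.
- *That the planned tests will point to the wrong sequence.* They could, but nothing in the documents shows that they will.
- *That the planned sample is enough to rank all four sequences.* About 0.20 SD is the unadjusted figure. After adjustment over six pairs, power for 0.20 SD is only 54%.

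Two further points stand. The added analysis must deal with missing week-12 scores and with people who leave before Level 2. And the SAP refers to a published protocol paper that is not among the documents, so the absence is shown for this document only.

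**Conclusion.** The gap is real but limited. The existing tests remain valid and answer the formal aims. No planned analysis estimates or compares the four whole sequences, although Section 1.1 says that the trial will identify a sequence for teletherapy systems. The data to be collected could give those estimates with useful but modest precision: between sequences with different starts, about 0.20 SD is detectable unadjusted (close to the 0.20 SD that the plan treats as clinically meaningful at Level 1) and about 0.25 SD with Bonferroni over six pairs. These figures rest on 1,000 evaluated, 32.4% non-response, 1:1 allocation at both levels, equal SDs and two-sided alpha of 0.05. They make no allowance for provider effects or for missing data beyond the planned dropout. This is an inexpensive improvement worth making, not a flaw in the existing comparisons.

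**What to change.** Add one row to Table 2, declared secondary or exploratory:

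- **Estimands:** mean week-12 PHQ-9 under each of the four embedded sequences.
- **Model:** weighted-and-replicated regression of PHQ-9 on sequence, at week 12 or on the repeated measures to week 12. The repeated-measures form fits better with the plan's use of all available data.
- **Weights:** inverse probability from the actual allocation ratios. If both levels are 1:1, these are 2 for responders (who count in both sequences they are consistent with) and 4 for re-randomised non-responders.
- **Standard errors:** robust, accounting for replication and for provider.
- **Missing data:** state how missing week-12 scores are handled, and how people who drop out before Level 2 are handled.
- **Reporting:** four sequence means with 95% confidence intervals, and pairwise differences with a named multiplicity adjustment.
- **Precision:** state both the unadjusted and the adjusted detectable difference.

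The cost is one more model on data already being collected, some specification work on weights and missing data, and a few extra comparisons that are less precise than the Level 1 contrast. If the row is not added, reword Section 1.1 so that the claim covers only the choice of step-up among non-responders.
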